2 SYNOPSIS

NAME OF COMPANY	SUMMARY TABLE	FOR NATIONAL
BioMarin Pharmaceutical Inc.	Referring to Part of the	AUTHORITY USE
[name]	Dossier:	ONLY:
[name]		
	Volume:	
NAME OF FINISHED PRODUCT:		
BMN 270	Page:	
NAME OF ACTIVE INCREDIENT.		
NAME OF ACTIVE INGREDIENT:	Reference:	
AAV5-hFVIII-SQ		

TITLE OF STUDY:

A Phase 3 Open-Label, Single-Arm Study To Evaluate The Efficacy and Safety of BMN 270, an Adeno-Associated Virus Vector–Mediated Gene Transfer of Human Factor VIII in Hemophilia A Patients with Residual FVIII Levels ≤ 1 IU/dL Receiving Prophylactic FVIII Infusions

PROTOCOL NUMBER:

270-301

STUDY SITES:

Approximately 60 sites worldwide.

PHASE OF DEVELOPMENT:

Phase 3

STUDY RATIONALE:

Hemophilia A (HA) is an X-linked recessive bleeding disorder that affects approximately 1 in 5,000 males. It is caused by deficiency in the activity of coagulation factor VIII (FVIII), an essential cofactor in the intrinsic coagulation pathway. This disorder can be either inherited, due to a genetic aberrancy, or an acquired immunologic process, leading to insufficient quantities of FVIII or a dysfunctional FVIII, but all are characterized by a defective coagulation process. The clinical phenotype of HA patients generally correlates tightly with the level of residual expression. Severe HA is classified as FVIII activity less than 1% of wild-type (< 1 IU/dL), moderate disease comprises 1-5% of wild-type activity and the mild form is 5-40% activity. The clinical manifestations of severe HA are frequent spontaneous bleeding episodes, predominantly in joints and soft tissues, with a substantially increased risk of death from hemorrhage when the brain is involved. Subjects with moderate disease can exhibit manifestations similar to those seen in patients with severe HA, resulting in a comparable bleeding phenotype.

Treatment of severe HA presently consists of intravenous injection of plasma-derived or recombinant human FVIII protein (rhFVIII) concentrates, both as prophylaxis 2-3 times per week, and at the time of a bleed, to prevent or control bleeding episodes, respectively. The half-life for FVIII (12 to 18 hours for most approved products) necessitates frequent infusions, and although a major advance in the treatment of HA, it remains common for severe HA patients to continue to have multiple bleeding events on prophylactic therapy (median ABR of 1-4 with prophylaxis treatment in a recently published retrospective observational study (Berntorp, 2017) and between 1-2 in 6 prospective FVIII interventional studies) and on-demand-only therapy (median ABR of 4.5-18 in a recently published retrospective study (Berntorp, 2017) and between 20-60 in

Page 6

NAME OF COMPANY	SUMMARY TABLE	FOR NATIONAL
BioMarin Pharmaceutical Inc.	Referring to Part of the	AUTHORITY USE
[name]	Dossier:	ONLY:
[name]		
NAME OF FINISHED PRODUCT:	Volume:	
BMN 270	Page:	
NAME OF ACTIVE INGREDIENT: AAV5-hFVIII-SQ	Reference:	

6 prospective FVIII interventional studies). The consequence of multiple bleeding events is the development of debilitating multiple-joint arthropathy and substantially increased risk of death. Chemical modification (eg, direct conjugation of polyethylene glycol (PEG) polymers) and bioengineering of FVIII (eg, FVIII-Fc fusion proteins) improve half-life by approximately 50%, and thus, show promise in reduced dosing and maintaining activity levels above a 1% trough for a greater proportion of the dosing interval. However, patients with severe HA who are treated with extended half-life FVIII remain dependent on multiple infusions to maintain critical levels of FVIII activity. There is therefore a strong unmet need for a fully preventive treatment of HA to give patients a FVIII level compatible with a normal and hemorrhage-free life.

Gene therapy offers the potential of disease-modifying therapy by continuous endogenous production of active FVIII following a single intravenous infusion of a vector encoding the appropriate gene sequence for long-term episomal expression. Hemophilia A is well-suited for a gene replacement approach because clinical manifestations are attributable to the lack of a single gene product (FVIII) that circulates in minute amounts (200 ng/ml) in the plasma. Tightly regulated control of gene expression is not essential, and even modest increases in the level of FVIII (any increase of the plasma level by 2 ng/ml induces an increase in activity of 1%) can ameliorate the severe form of hemophilia A. Thus, relatively small changes in endogenous FVIII activity can result in clinically relevant improvements in disease phenotype. Finally, the circulating FVIII response to gene transduction can be assessed using validated quantitative rather than qualitative endpoints that are easily assayed using established laboratory techniques.

Several different gene transfer strategies for FVIII replacement have been evaluated, but adeno-associated viral (AAV) vectors show the greatest promise. They have an excellent and well-defined safety profile, and can direct long-term transgene expression with tropism and promoter specificity for specific tissues, such as the liver (for serotypes 2, 5 and 8 among others). Indeed, an ongoing gene therapy clinical trial for a related disorder, hemophilia B, has established that stable (median follow-up of 3.2 years) expression of human factor IX (hFIX) at levels that are sufficient for conversion of their bleeding phenotype from severe to moderate or mild is achievable following a single peripheral vein infusion of AAV8-hFIX vector. Several participants in this trial have been able to discontinue factor prophylaxis without suffering spontaneous hemorrhages, even when they undertook activities that previously resulted in bleeding. Thus, gene therapy treatment has resulted in a substantial improvement in their quality of life (Nathwani, 2014).

[figure not shown]
BMN 270 is an AAV5-based gene therapy vector that expresses the SQ form of hFVIII under the control of a hybrid human liver-specific promoter (Figure 1).

Page 7

NAME OF COMPANY	SUMMARY TABLE	FOR NATIONAL
BioMarin Pharmaceutical Inc.	Referring to Part of the	AUTHORITY USE
[name]	Dossier:	ONLY:
[name]		
	Volume:	
NAME OF FINISHED PRODUCT:		
BMN 270	Page:	
NAME OF ACTIVE INGREDIENT: AAV5-hFVIII-SQ	Reference:	

Figure 1. hFVIII-SQ Vector Genome Schematic

Legend –Note that schematic is not to scale; nt = nucleotides

BMN 270 will be delivered by a single intravenous dose and is designed to achieve stable, potentially life-long expression of active hFVIII in the plasma, synthesized from vector-transduced liver tissue.

BMN 270 is being evaluated in clinical study 270-201, an ongoing first-in-human, phase 1/2 dose escalation study in subjects with severe HA designed to assess the safety and efficacy of BMN 270 at various dose levels (6E12 vg/kg, 2E13 vg/kg, 4E13 vg/kg, 6E13 vg/kg). Specifically, 270-201 explores the relationship of vector dose to the augmentation of residual FVIII activity and whether these levels are sufficient to alter the clinical phenotype. Preliminary results from 270-201 have demonstrated that following gene transfer, FVIII activity above 15% (15 IU/dL) and, in many cases, within the normal range for FVIII, is achievable with a dose of 4-6E13 vg/kg with an acceptable safety profile (Pasi, 2017).

The current study is a Phase 3, single-arm, open-label study designed to assess whether, in an expanded sample, BMN 270 can safely alter the clinical phenotype of hemophilia A patients with residual FVIII activity $\leq 1 \text{ IU/dL}$.

OBJECTIVES:

The primary efficacy objective of the study is to:

• Assess the efficacy of BMN 270 defined as FVIII activity, as measured by one-stage clotting assay, during Weeks 49-52 following intravenous infusion of BMN 270

The secondary efficacy objectives of the study are to:

 Assess the impact of BMN 270 on usage of exogenous FVIII replacement therapy from Week 5 to Week 52

Page 8

NAME OF COMPANY	SUMMARY TABLE	FOR NATIONAL
BioMarin Pharmaceutical Inc.	Referring to Part of the	AUTHORITY USE
[name]	Dossier:	ONLY:
[name]		
	Volume:	
NAME OF FINISHED PRODUCT:		
BMN 270	Page:	
NAME OF A CTUVE DIGDEDIENT		
NAME OF ACTIVE INGREDIENT:	Reference:	
AAV5-hFVIII-SQ		

• Assess the impact of BMN 270 on the number of bleeding episodes requiring exogenous FVIII replacement therapy from Week 5 to Week 52

The tertiary efficacy objective of the study is to:

• Assess the impact of BMN 270 on patient-reported outcomes (PROs) at Week 52 of the study compared to baseline

The safety objectives of the study are to:

- Evaluate the safety of BMN 270 during the first 52 weeks following intravenous infusion
- Assess the long-term safety of BMN 270

STUDY DESIGN AND PLAN:

[figure not shown]
This is a Phase 3, single-arm, open-label study in hemophilia A patients with residual FVIII levels ≤ 1 IU/dL treated continuously with prophylactic exogenous FVIII for a minimum of one year prior to enrollment. Subjects will be enrolled at approximately 60 sites worldwide. Subjects must have high-quality, well-documented historical data available concerning previous bleeding episodes and exogenous FVIII usage over the previous 12 months in order to be eligible to enroll in the study.

Approximately 130 adult subjects with severe HA will receive a 6E13 vg/kg dose of BMN 270 as a single intravenous infusion. Approximately 20 subjects will enroll in the study with at least 12 months of well-documented high-quality historical data concerning previous bleeding episodes and exogenous FVIII usage, while approximately 110 subjects will enroll in the study after having completed approximately 6 months' participation in the BioMarin-sponsored non-interventional study 270-902.

Page 9

NAME OF COMPANY **SUMMARY TABLE** FOR NATIONAL BioMarin Pharmaceutical Inc. **AUTHORITY USE** Referring to Part of the [name] Dossier: **ONLY:** [name] Volume: NAME OF FINISHED PRODUCT: **BMN 270** Page: NAME OF ACTIVE INGREDIENT: Reference: AAV5-hFVIII-SQ

yo v years old, HA v hemophilis A. FVIII r factor VIII, Px v prophylaxis, AAV5 v adeno-associated virus, senetype 5, TAb v total antibody, mo v month, vg v vactor genomes, tg = kilogram, #/u = follow-up

The Data Monitoring Committee (DMC) will review available safety and efficacy (eg, FVIII activity) data during the study on an ongoing basis and may determine, based on emerging data and the risk/benefit profile, that further enrollment at 6E13 vg/kg should be discontinued in favor of a different dose of BMN 270, not to exceed 6E13 vg/kg. If the DMC recommends a dosing modification, then additional subjects may be enrolled, up to a total of approximately 130 subjects, at the new BMN 270 dose level (regardless of the number of subjects previously enrolled at 6E13 vg/kg).

An interim analysis is planned after 20 treated subjects have completed the Week 26 visit. The final analysis for the study will be performed after all subjects have been followed for 52 weeks post-BMN 270 infusion. After the final analysis, safety and efficacy will then continue to be assessed long-term in all subjects for a total of approximately 5 years.

To avoid breakthrough bleeding, subjects will only discontinue exogenous prophylactic FVIII replacement therapy after FVIII activity has reached at least 5 IU/dL or 4 weeks following infusion of BMN 270, whichever is earlier. Four weeks represents the time by which endogenous production of FVIII following gene transfer is expected to be efficacious.

Throughout the study, subjects with FVIII activity below 5 IU/dL may be monitored more frequently at the discretion of the Medical Monitor and the Investigator. In subjects who show an initial response to BMN 270 but who later have FVIII activity decline to < 5 IU/dL, the investigator and Medical Monitor will review the subject's FVIII activity level trends (not specific FVIII activity levels) and discuss whether to resume prior FVIII prophylaxis. In addition, the

Page 10

NAME OF COMPANY	SUMMARY TABLE	FOR NATIONAL
BioMarin Pharmaceutical Inc.	Referring to Part of the	AUTHORITY USE
[name]	Dossier:	ONLY:
[name]		
	Volume:	
NAME OF FINISHED PRODUCT:		
BMN 270	Page:	
NAME OF ACTIVE INGREDIENT: AAV5-hFVIII-SQ	Reference:	

investigator will notify the subject of his FVIII activity levels and will discuss with the subject the risk of bleeding and when (and if) prior FVIII prophylaxis will be resumed.

There will be an ongoing review of individual subject safety by the Medical Monitor, and both safety and efficacy data by the DMC. FVIII activity by a validated assay will be used to evaluate efficacy over the course of the study. Therapeutic oral corticosteroids may be initiated when a subject's ALT values are elevated or based on review of FVIII activity and liver enzyme data, and subsequent dosage adjustments made, after consultation between the Investigator and the Medical Monitor.

Any safety signal may trigger a review of the data and possible additional immunogenicity studies or other diagnostics deemed necessary that include an assessment of cellular immune responses using collected peripheral blood mononuclear cells (PBMCs).

NUMBER OF SUBJECTS PLANNED:

Approximately 130 subjects may enroll into the study.

DIAGNOSIS AND ALL CRITERIA FOR INCLUSION AND EXCLUSION:

Patients are eligible to be included in the study only if all of the following criteria apply:

- 1. Males \geq 18 years of age with hemophilia A and residual FVIII levels \leq 1 IU/dL as evidenced by medical history, at the time of signing the informed consent.
- 2. Must have been on prophylactic FVIII replacement therapy for at least 12 months prior to study entry. High-quality, well-documented historical data concerning bleeding episodes and FVIII usage over the previous 12 months must be available.
- 3. Treated/exposed to FVIII concentrates or cryoprecipitate for a minimum of 150 exposure days (EDs).
- 4. Willing and able to provide written, signed informed consent after the nature of the study has been explained and prior to any study-related procedures.
- 5. No previous documented history of a detectable FVIII inhibitor, and results from a Bethesda assay or Bethesda assay with Nijmegen modification of less than 0.6 Bethesda Units (BU) (or less than 1.0 BU for laboratories with a historical lower sensitivity cutoff for inhibitor detection of 1.0 BU) on 2 consecutive occasions at least one week apart within the past 12 months (at least one of which should be tested at the central laboratory).

Page 11

NAME OF COMPANY	SUMMARY TABLE	FOR NATIONAL
BioMarin Pharmaceutical Inc.	Referring to Part of the	AUTHORITY USE
[name]	Dossier:	ONLY:
[name]		
	Volume:	
NAME OF FINISHED PRODUCT:		
BMN 270	Page:	
NAME OF ACTIVE DIGDEDIENT		
NAME OF ACTIVE INGREDIENT:	Reference:	
AAV5-hFVIII-SQ		

- 6. Sexually active participants must agree to use an acceptable method of effective contraception, either double-barrier contraception (ie, condom + diaphragm; or condom or diaphragm + spermicidal gel or foam) or their female partner either using hormonal contraceptives or having an intrauterine device. Participants must agree to contraception use for at least 12 weeks post-infusion; after 12 weeks, subjects may stop contraception use only if they have had 3 consecutive semen samples with no detectable viral vector DNA.
- 7. Willing to abstain from alcohol consumption for at least the first 52 weeks following BMN 270 infusion.
- 8. HIV positive patients may be enrolled, only if the patient has a CD4 count > 200/mm³ and an undetectable viral load (unquantifiable viral load as defined as less than the limit of quantification by the testing laboratory's assay is permitted)

Patients are excluded from the study if any of the following criteria apply:

- 1. Detectable pre-existing antibodies to the AAV5 capsid.
- 2. Any evidence of active infection or any immunosuppressive disorder, except for HIV infection as described in the inclusion criterion above.
- 3. Significant liver dysfunction with any of the following abnormal laboratory results:
- ALT (alanine transaminase) or AST >2X ULN;
- Total bilirubin >2X ULN;
- Alkaline phosphatase >2X ULN; or
- INR (international normalized ratio) ≥ 1.4 .

Subjects whose liver laboratory assessments fall outside of these ranges may undergo repeat testing and, if eligibility criteria are met on retest, may be enrolled after confirmation by the Medical Monitor. In addition, subjects with abnormal laboratory results related to confirmed benign liver conditions are considered eligible for the study notwithstanding their abnormal laboratory results and may be enrolled after discussion with the Medical Monitor.

Page 12

NAME OF COMPANY	SUMMARY TABLE	FOR NATIONAL
BioMarin Pharmaceutical Inc.	Referring to Part of the	AUTHORITY USE
[name]	Dossier:	ONLY:
[name]		
	Volume:	
NAME OF FINISHED PRODUCT:		
BMN 270	Page:	
NAME OF ACTIVE DIGDEDIENT		
NAME OF ACTIVE INGREDIENT:	Reference:	
AAV5-hFVIII-SQ

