9.4.8.1 Concomitant Hemophilia Treatments

Subjects on prophylactic FVIII therapy will discontinue their regular treatment regimen starting 4 weeks after the day of infusion or after FVIII activity has reached at least 5 IU/dL (whichever is earlier) and switch to an "on-demand" schedule. FVIII replacement therapy can always be taken as needed by the subject for treatment of an acute bleeding episode; the subject must carefully record his treatment and bleeding episodes in his diary. Prophylactic FVIII use can be used on a case-by-case basis and in consultation with the Medical Monitor to prevent bleeding in extenuating circumstances (eg, peri-operative).

In addition, information on FVIII usage and bleeding episodes by medical history must be well-documented and available and will be collected from subjects for the 12-month period immediately preceding study enrollment. Further information on the details that should be provided as part of the subject's well-documented medical and FVIII usage history are provided in the On Site File Binder.

In order to enable rigorous comparisons of pre-study versus on-study FVIII usage and bleeding episodes, the Medical Monitor will review each screened patient's prior bleed and hemophilia medication logs to determine if they are of "high-quality". Elements that will be assessed to judge the quality of such historical data may include, but are not limited to, the following:

- Date, type (eg, joint, muscle, other), location of bleeds
- Date, name, dose (calculated in IU/kg), and reason for use (eg, usual prophylaxis, one-time prophylaxis, treatment for bleed, surgery) of hemophilia medications.

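### In the text shown, the 5 IU/dL limb of the prophylaxis-stopping rule sets no time since the last FVIII dose, so infused factor can meet it in Weeks 1-3; the result is a bounded early stop.

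*Protocol*

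**What the plan says.** The Amendment 2 synopsis (Study Design and Plan) allows subjects to discontinue prophylaxis only "after FVIII activity has reached at least 5 IU/dL or 4 weeks following infusion of BMN 270, whichever is earlier". Section 9.1 of Amendment 1 has the same rule. Section 9.4.8.1 of Amendment 1 turns it into an instruction to end the regular regimen and go to on-demand treatment at 4 weeks "or after FVIII activity has reached at least 5 IU/dL", again whichever comes first. The stated purpose is to prevent breakthrough bleeds. The synopsis then explains the 4-week limb: "Four weeks represents the time by which endogenous production of FVIII following gene transfer is expected to be efficacious".

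Table 9.1.2 of Amendment 1 schedules FVIII assays at Days 8, 15, 22 and 29, with windows of 48 hours either side.

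Elsewhere the protocol does control for infused factor. Table 9.1.1 footnote b (Amendment 1) requires the baseline value to be a trough, more than 72 hours or 5 half-lives after the last dose. Section 9.7.2.1 (Amendment 1) drops efficacy values obtained within 72 hours of an infusion. The one wash-out request attached to post-treatment assays (Table 9.1.2 footnote c and Section 9.7.2.1, Amendment 1) is confined to subjects who had reached 5 IU/dL at Week 16 and had not gone back to FVIII.

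**The concern.** The 5 IU/dL limb exists to detect expression that arrives before four weeks. It operates while the subject is still infusing FVIII, and an activity assay does not separate infused from endogenous factor. With no condition on time since the last dose, a reading on Day 8, 15 or 22 can reach 5 IU/dL from concentrate alone. The Week 16 restriction means that the existing wash-out request does not help at these visits.

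A subject with little or no expression could then be moved to on-demand treatment early, against the rule's own purpose. Low expression at this stage need not mean eventual failure, because the protocol itself expects efficacious production only by about Week 4. The later safeguard is partial: it applies "In subjects who show an initial response to BMN 270 but who later have FVIII activity decline to < 5 IU/dL", which a falsely triggered subject may never truly have shown, and it leads to a review of "FVIII activity level trends (not specific FVIII activity levels) and discuss whether to resume prior FVIII prophylaxis", not to automatic resumption.

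**Working it through.** The plan gives no figure to reproduce. The check asks whether infused factor can plausibly read 5 IU/dL at an untimed visit, and for how long an early stop could last.

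**Inputs from the protocol (Amendment 2 synopsis, Study Rationale).** Half-life h: "The half-life for FVIII (12 to 18 hours for most approved products) necessitates frequent infusions". Frequency: "both as prophylaxis 2-3 times per week", so an even interval τ of 168/3 = 56 h or 168/2 = 84 h.

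**Assumed input.** Trough T = 1 IU/dL at the end of the interval. The synopsis mentions that level only as background on extended half-life products, "maintaining activity levels above a 1% trough for a greater proportion of the dosing interval". It is not a value for enrolled subjects, so T is also varied from 0.5 to 2 IU/dL. Endogenous FVIII is set to zero.

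**Formula.** With single-compartment decay, infused factor is below 5 IU/dL for the last h × log2(5/T) hours. The share of the interval at or above 5 IU/dL is 1 − h × log2(5/T)/τ, floored at 0.

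For T = 1, log2(5) = 2.32, so the time below 5 IU/dL is 12 × 2.32 = 27.9 h or 18 × 2.32 = 41.8 h.

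| τ | h | T = 1 | T = 0.5 | T = 2 | implied peak at T = 1 |
|---|---|---|---|---|---|
| 56 h | 12 h | (56 − 27.9)/56 = 0.50 | 0.29 | 0.72 | 25 IU/dL |
| 56 h | 18 h | (56 − 41.8)/56 = 0.25 | 0.00 | 0.58 | 9 IU/dL |
| 84 h | 12 h | (84 − 27.9)/84 = 0.67 | 0.53 | 0.81 | 128 IU/dL |
| 84 h | 18 h | (84 − 41.8)/84 = 0.50 | 0.29 | 0.72 | 25 IU/dL |

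The range is 25-67% at T = 1, and 0-81% for T between 0.5 and 2 IU/dL.

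**Cross-check from an assumed peak P of 20-100 IU/dL.** Time at or above 5 IU/dL is h × log2(P/5): 24 to 52 h at h = 12, and 36 to 78 h at h = 18. That is 43-100% of a 56 h interval and 29-93% of an 84 h interval. Both routes say that a false reading is possible over most of the plausible range; neither gives a rate for this trial.

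**Duration of an early stop.** The next assay is 7 days later, or 3 to 11 days with both windows used. After 168 h, infused factor has passed through 168/18 = 9.3 to 168/12 = 14 half-lives, so that reading is essentially endogenous. If it is acted on, the excess time off prophylaxis is about a week. The ceiling is Day 29 − Day 8 = 21 days. It needs an immediate stop on Day 8 and no action on the Day 15 and Day 22 values.

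**Effect of a time condition.** For infused factor alone to read 5 IU/dL at 72 h, the peak would have to be 5 × 2^(72/12) = 320 IU/dL at h = 12, or 5 × 2^(72/18) = 80 IU/dL at h = 18. An assumed peak of 100 IU/dL at h = 18 leaves 100 × 2^−4 = 6.3 IU/dL at 72 h and 100 × 2^−5 = 3.1 IU/dL at 90 h. This is why 5 half-lives should apply where it is longer than 72 h.

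**The case against.** The strongest reply is that the operative wording is not visible. Only part of the Amendment 2 synopsis is shown, the section text comes from Amendment 1, the note to file names a version 7.0, and Section 9.7.2.1 sends sample-collection details to a Laboratory Manual. A timing condition could sit in any of these. That stands as a caveat on the point, but it does not repair the rule in the text at hand.

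Second, context favours a sensible reading: the aim is to avoid bleeds and the next sentence speaks of endogenous production. That shows the intent, but an instruction to discontinue at a threshold should say which readings count, as the protocol does for baseline and for efficacy values.

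Third, a reader might infer from the 25-67% figure that a quarter to two thirds of subjects would be stopped wrongly. The documents do not support that. The 1 IU/dL trough is an assumption, the figure is conditional on zero expression, its ends imply peaks as far apart as 9 and 128 IU/dL, and the share of subjects below 5 IU/dL endogenous at Days 8-22 is not given.

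Fourth, the harm is limited, and this stands. The 4-week limb takes everyone off prophylaxis regardless of expression. FVIII is assayed weekly, and subjects below 5 IU/dL may be monitored more often. On-demand FVIII is always available, prophylactic FVIII is allowed case by case (Section 9.4.8.1), and early consultation is encouraged (Section 9.7.3.1).

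Finally, the Week 16 limit on wash-out may be a deliberate choice to avoid withholding factor early. That argues against skipping doses to obtain a sample. It does not argue against restricting which samples count.

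**Conclusion.** The point holds in a limited form. In the Amendment 2 synopsis and in Sections 9.1 and 9.4.8.1 of Amendment 1, the 5 IU/dL limb carries no condition on time since the last exogenous dose, and no wash-out text shown covers Weeks 1-3. A reading raised by infused factor can therefore end prophylaxis early in a subject with little expression, typically by about a week and by at most about 21 days.

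It should be fixed because the rule as written can work against its own purpose, but it is a bounded bleeding-safety issue. A reader might also infer that the efficacy results are compromised. They are not directly biased: bleeding and FVIII use count from Week 5, after the 4-week stop, and the FVIII activity endpoint has its own 72-hour exclusion. How often a false trigger would occur cannot be derived from the documents, and the percentages above only show that it is plausible. Confidence is medium, because the Amendment 2 body, later versions and the Laboratory Manual are not shown.

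**What to change.** Wherever the rule appears (synopsis, Sections 9.1 and 9.4.8.1), add that a value of 5 IU/dL or more counts only if the sample was either:

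- taken at least 72 h after the last exogenous FVIII dose, or 5 half-lives of the product used if that is longer (90 h at an 18 h half-life); or
- taken pre-dose at the end of the usual dosing interval, in a subject whose already documented pre-treatment trough on that regimen was below 5 IU/dL.

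Doses are not to be skipped to obtain such a sample. Without one, prophylaxis stops at 4 weeks.

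The second option is needed because an even three-times-weekly interval (56 h) never reaches 72 h, and an even twice-weekly interval (84 h) falls short of 90 h. It ensures that infused factor on the usual regimen would not by itself explain the reading; it does not guarantee 5 IU/dL of endogenous activity.

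The cost is one added provision in each place, plus setting the weekly visit before a dose within the existing 48-hour window. Infusions are already recorded in the diary. The downside is that some subjects, mainly those on three doses a week without a documented trough, continue their usual prophylaxis until Week 4.
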